4.0 Clinical Protocol

4.1 Study Design and Scope

This is a prospective, multi-center, clinical study designed to evaluate the safety and efficacy of the Accent MRI System in a patient population indicated for implant of a pacemaker within and outside of the MRI environment.

The study will be conducted at a minimum of 60 centers and a maximum of 80 centers worldwide. The minimum requirement for completing this study is 800 patients. A maximum of 120 (15% of the total) enrollments will be allowed per center. It is anticipated that at least 30% of enrollments will include patients implanted with the Tendril MRI lead in the right atrium.

Within the MRI environment, The Accent MRI system will be evaluated in conjunction with the MRI Activator. The MRI Activator performance will be evaluated qualitatively during this phase of the study. Up to 363 patients, including patients who were randomized to the MRI Control Group in previous versions of the investigational plan, will be enrolled in this phase of the study.

Enrollment in the MRI clinical study is expected to take approximately 12 months. The anticipated duration of this study is 32 to 34 months, depending on the rate of enrollment. All patients will be implanted with an Accent MRI pacemaker and a Tendril MRI lead. Devices implanted outside the United States will utilize different device model numbers.

The following study evaluations will occur after implant:

- Post implant follow up (pre-discharge)
- 2 month visit (post implant, in-office)
- 6 month visit (post implant, in-office)
- 12 months visit (post implant, in-office)
- Every 6 months post implant until study completion

MRI visits will consist of:

- MRI visit which includes:
 - Pre-MRI scan testing
 - MRI scan
 - post MRI testing
- 1 month post MRI visit

The schedule of follow up visits for the lead safety component of the study is based on the date of implant of the Accent MRI System. The follow up schedule for the MRI visit is based on the date of implant or revision of an MRI lead until the MRI visit; the MRI visit should take place no sooner than one week after the 2 month post implant or system revision procedure where the Tendril MRI lead was implanted, repositioned or replaced. The one month post MRI follow up visit is based on the MRI visit.

Figure 2: Lead Safety Phase Flow Diagram

[figure not shown]
[figure not shown]

Figure 3: MRI Phase Flow Diagram

4.2 Objectives/Study Endpoints

The primary objectives of this study are to assess the safety and efficacy of the Accent MRI™ system in a patient population that is indicated for a pacemaker.

Primary Endpoints

Lead Safety

Safety of the Tendril MRI™ lead will be evaluated in terms of freedom from RA and RV lead-related complications for the acute (implant to 2 month visit) and chronic (2 month visit through the 12 month visit) timeframes.

MRI Safety

The safety of the Accent MRI system will be evaluated in terms of freedom from MRI scan related complications in the month following the MRI scan.

Lead Efficacy

Efficacy of the Tendril MRI™ lead will be evaluated in terms of the change in bipolar atrial and ventricular capture and sensing thresholds before and after the MRI scan.

Secondary Endpoints

Safety

Safety of the Accent MRI™ system will be evaluated in terms of freedom from system-related complications through the 12 month visit.

Efficacy

Efficacy of the Tendril MRI™ lead will be evaluated in terms of the bipolar atrial and ventricular capture thresholds at the MRI Visit.

4.2.1 Primary Lead Safety Endpoints

4.2.1.1 Freedom from RA lead-related complications in the acute period

4.2.1.2 Freedom from RV lead-related complications in the acute period

The lead safety endpoint will be assessed separately for the RA and RV leads and for an acute (implant to 2 months) period.

The hypothesis is formally expressed as:

H₀: Freedom from lead related complications from implant up to 2 month visit \leq 92%

H_a: Freedom from lead related complications from implant up to the 2 month visit $>$ 92%

The objective performance criterion of 92% used for this objective denotes the minimum level of adequate safety for the RA or RV leads in the acute time period. This endpoint will be tested separately for the RA and the RV leads. Only those complications occurring by the 2 month visit and adjudicated by the Clinical Events Committee as RA lead or RV lead complications will be used in the estimation of these endpoints.

Sample Size

Simulation was used to calculate the sample size requirements for testing the Kaplan-Meier estimated survival probability for the freedom-from-complication endpoint. The SCORE Registry, containing patients who were implanted with a St. Jude Medical RA and RV market approved Tendril™ family of leads, was used to estimate freedom from lead related complications in the acute time period. Using these estimates derived from the SCORE Registry data, the expected proportion of patients free from RA lead related complications from implant to 2 months is 0.995 with 95% lower confidence bound of 0.994. Similarly, for the RV lead, the expected proportion of patients free from RV lead related complications from implant to 2 months is 0.993 with 95% lower confidence bound of 0.991. Taking a conservative expected complication free rate of 0.97, with a study size of 800 RV leads and 400 RA leads patients and a Type 1 error rate for the acute time period hypothesis test of $\alpha = 0.025$ for a one-sided test, the power is greater than 98%.

Patient Group

All patients that have had an attempted implant or a successful implant of an Accent MRI system will be included in this endpoint.

Patients who are lost to follow-up or withdrawn prior to the 2 month follow-up visit due to an RA or RV lead related complication will be analyzed as having experienced a complication at the date the complication occurred. Patients who withdraw for reasons unrelated to an RA or RV lead related complication will be censored at the date of withdrawal.

Analysis

The desired outcome is to reject both null hypotheses for the RA and RV endpoints. The RA and RV hypothesis will be tested separately. The null hypothesis for the RA or RV endpoints will be rejected at the 2.5% significance level if the 95% lower limit of a two-sided confidence interval for the freedom from RA or RV lead-related complications by 2 months is greater than 92%. The confidence

interval will be constructed using the log-log transformation of the event free estimate at 2 months.

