4.2.1.3 Freedom from RA lead-related complications in the chronic time period

4.2.1.4 Freedom from RV lead-related complications in the chronic time period

The lead safety endpoint will be assessed separately for the RA and RV leads for the chronic (2 months through the 12 month visit) time period.

The hypothesis is formally expressed as:

H₀: Freedom from lead related complications from the 2 month through the 12 month visit \leq 95%

H_a: Freedom from lead related complications from the 2 month through the 12 month visit $>$ 95%

The objective performance criterion of 95% used for this objective denotes the minimum level of adequate safety for the RA or RV leads in the chronic time period. This endpoint will be tested separately for the RA and the RV leads. Only those complications occurring by the 12 month visit and adjudicated by the Clinical Events Committee as RA lead or RV lead complications will be used in the estimation of these endpoints.

Sample Size

Simulation was used to calculate the sample size requirements for testing the Kaplan-Meier estimated survival probability for the freedom-from-complication endpoint. The SCORE Registry, containing patients who were implanted with an RA and RV market approved Tendril™ family of leads, was used to estimate freedom from lead related complications in the chronic time period. Using these estimates derived from the SCORE registry data, the expected proportion of patients free from RA lead related complications from 2 months post-implant through 12 months is 0.996 with a 95% lower confidence bound of 0.994. Similarly, for the RV lead, the expected proportion of patients free from RV lead related complications from 2 months post-implant through 12 months is 0.998 with 95% lower confidence bound of 0.997. Taking a conservative expected complication free rate of 0.98, with a study size of 800 RV leads and 400 RA leads patients and a Type 1 error rate for the chronic time

period hypothesis test of $\alpha = 0.025$ for a one-sided test, the power is greater than 98% for the RV leads and greater than 85% for the RA leads.

Patient Group

All patients who have had an attempted implant or a successful implant of an Accent MRI system will be included in this endpoint.

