- Have a pacing threshold difference not exceeding 0.5 V at 0.5 ms between the two-month and MRI visit device pre-check, in cases where the MRI visit occurs approximately 9-12 weeks after the implant or system revision procedure since such short-term variability in pacing performance can be indicative of an abnormal lead/tissue interface that could confound analyses of MRI related effects.
- Have an atrial lead to be included in the '% success (change in atrial capture threshold)' endpoint analysis and/or a ventricular lead to be included in the '% success (change in ventricular capture threshold)' endpoint analysis
- Are not in AF at the time of atrial capture threshold measurements. Note: If atrial arrhythmias persist throughout the visit window for the MRI and/or 1 Month Post MRI visit, and no atrial capture threshold value can be obtained either at the MRI and/or 1 Month Post MRI visit, measured atrial capture threshold values from the next nearest timed visit may be substituted.

The proportion of patients not experiencing increases of 0.5V at 0.5ms for both atrial and ventricular capture thresholds will be calculated separately along with the associated 2.5% lower confidence bound. The lower bound for both of these proportions will be compared to the

OPC of 90%. The endpoints will be considered successful if the lower bound is greater than 90%.

Additional Analyses

A sensitivity analysis of the endpoint will be conducted using the ITT population, where both a worst and best case analysis will be performed. The worst case analysis will consist of treating all missing data as failures. The best case analysis will treat all missing data as successes.

4.2.3.3 Proportion of patients with atrial sensing amplitude decrease of $\leq 50\%$ and a sensing amplitude at 1-month post MRI visit of $\geq 1.5\text{mV}$

The hypothesis for the atrial sensing threshold is formally expressed as:

H₀: Proportion of patients with an atrial sensing amplitude decrease of $\leq 50\%$ and atrial sensing amplitude at 1-month post MRI visit of $>1.5\text{ mV} \leq 85\%$

H_a: Proportion of patients with an atrial sensing amplitude decrease of $\leq 50\%$ and atrial sensing amplitude at 1-month post MRI visit of $\geq 1.5\text{ mV} > 85\%$

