The analysis will be conducted on the per-protocol population. The per-protocol population includes patients who meet the following criteria:

- Successfully implanted with the Accent MRI™ system
- Have MRI visit data
- Meet the MRI Conditions of Use
- Received an MRI scan (if in the MRI group)
- Have 1-month post MRI visit data
- Have a pacing threshold difference not exceeding 0.5V between the two-month and three month post-implant (MRI scan pre-check), in cases where the MRI visit takes place approximately 9-12 weeks after an implant or system revision procedure since such short-term variability in pacing

performance can be indicative of an abnormal lead/tissue interface that could confound analyses of MRI related effects.

- Have a pre-MRI/pre-waiting period sensing amplitude greater than or equal to 5.0 mV in the ventricle or greater than or equal to 1.5 mV in the atrium.
- Have an atrial lead to be included in the ‘% success (change in atrial sensing amplitude)’ endpoint analysis and/or a ventricular lead to be included in the ‘% success (change in ventricular sensing amplitude)’ endpoint analysis
- Are not in AF at the time of atrial sensing amplitude measurements
- Have an intrinsic heart rate ≥ 30 beats per minute at the time of ventricular and/or atrial capture threshold measurements

The proportion of patients not experiencing an atrial sensing amplitude decrease of $\leq 50\%$ and atrial sensing amplitude at 1-month post MRI visit of >1.5 mV will be calculated. The associated 2.5% lower confidence bound will also be derived. This lower bound will be compared to the OPC of 85% and the endpoint will be considered successful if the lower bound is greater than 85%.

The proportion of patients not experiencing a ventricular sensing amplitude decrease of $\leq 50\%$ and ventricular sensing amplitude at 1-month post MRI visit of > 5 mV will be calculated. The associated 2.5% lower confidence bound will also be derived. This lower bound will be compared to the OPC of 87% and the endpoint will be considered successful if the lower bound is greater than 87%.

All individual primary efficacy endpoints must be successful (reject the null hypothesis at the $\alpha = 2.5\%$ level) for the efficacy endpoint to be successful.

Additional Analyses

The same additional analyses described above in section 4.2.3.1 and 4.2.3.2 will be completed for this endpoint if required.

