4.4.2 Implant Procedures

Perform the device and lead implant procedure according to standard of care. Do not implant a dual chamber device with only one lead. Consult the User's Manual for implantation guidelines, appropriate lead/device connections and general handling information. The Accent MRI system will be considered successfully implanted if, at a minimum, the Accent MRI pacemaker and a Tendril MRI lead are implanted.

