4.4.2.1 Lead Placement and Testing

Implant one Tendril MRI™ Lead (Model LPA1200M) in the right ventricle and one in the right atrium for dual chamber pacemakers. Implant one Tendril MRI™ lead in the right ventricle for single chamber pacemakers. The physician can use any appropriate delivery system that is legally marketed from St. Jude Medical or any other manufacturers.

- Only Tendril MRI™ leads are permitted (abandoned leads, additional leads and non-Tendril MRI™ leads are not permitted). If non-Tendril MRI™ leads are implanted, complete a protocol deviation form.
- Use of lead extenders or adaptors is not permitted. If used, complete a protocol deviation form.
- The atrial or ventricular port cannot be plugged. If either port is plugged, complete a protocol deviation form.

After the lead(s) are connected to the device, obtain the following electrical measurements for the RA and/or RV leads.

- Manual bipolar capture threshold at a pulse width of 0.5 ms using the Decrement Threshold test method. Pace at least three cycles per step, and confirm at least three consecutive beats have capture before recording the capture threshold results.
- Bipolar sensing amplitude using the Incremental Test Method. Set the required sensed beats to at least 3 cycles per step. Confirm at least three consecutive beats are sensed before recording the sensing threshold results.
- Bipolar lead impedance

Note: RA lead measurements are not required if a single chamber device is implanted. RA capture and sensing thresholds are not required if a patient is in atrial fibrillation or atrial flutter.

RA/RV sensing measurements are not required if the patient's intrinsic rate has been established to be below 30 beats per minute. RV capture thresholds are not required if a high ventricular rate is present.

Data Submission

Once required testing has been completed at the Implant Visit, complete and submit the forms listed below to St. Jude Medical. Upload device session records through the EDC study site portal. Device session records may also be sent to St. Jude Medical, CRMD Sylmar, CA.

- Enrollment Form
- Implant Form
- Medication Log
- Adverse Event Form, if applicable

- Protocol Deviation Form, if applicable
- Product Out of Service Form, if applicable
- Death Form, if applicable

It is recommended that the following device printouts and measurements be maintained at the site.

- FastPath Summary
- Test Results with Large Freezes, Include Battery & Leads

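### The RA-lead safety endpoints, as written, include patients with no RA lead; if followed, this conflicts with the 400-RA-lead power basis and removes type I error control

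*Combined protocol and SAP*

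**What the plan says.** The Patient Group paragraph for the acute endpoints (4.2.1.1 and 4.2.1.2) serves both leads: "All patients that have had an attempted implant or a successful implant of an Accent MRI system will be included in this endpoint". The chronic paragraph (4.2.1.3 and 4.2.1.4) is almost identical: "All patients who have had an attempted implant or a successful implant of an Accent MRI system will be included in this endpoint". Neither requires the lead under test to be present. The text that follows each paragraph deals only with withdrawal and censoring, and removes nobody for lack of an RA lead.

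Section 4.4.2 sets the threshold for a system implant at one lead: "The Accent MRI system will be considered successfully implanted if, at a minimum, the Accent MRI pacemaker and a Tendril MRI lead are implanted". Section 4.4.2.1 says which lead that is for single-chamber devices: "Implant one Tendril MRI™ lead in the right ventricle for single chamber pacemakers". Single-chamber patients are therefore in the RA Patient Group without an RA lead.

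The sample-size text uses a per-lead basis, "with a study size of 800 RV leads and 400 RA leads patients", and for the chronic period "the power is greater than 98% for the RV leads and greater than 85% for the RA leads". The criteria of 92% and 95% are described as minimum safety levels for the RA or RV leads. Section 4.1 requires 800 patients in total, anticipates at least 30% with an RA lead, and sets no minimum number of RA leads.

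The MRI efficacy endpoints in 4.2.3 do carry the missing condition. Their per-protocol lists include "Have an atrial lead to be included in the" for atrial capture, with a matching item for the atrial sensing endpoint.

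**The concern.** A patient with no RA lead contributes follow-up time but cannot have the event. In the RA Kaplan-Meier estimate, each such patient pulls the curve towards 100%. On the literal set, the quantity tested is the share of all study patients without an RA-lead complication, whereas the 92% and 95% criteria are meant for the lead.

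This affects two of the nine primary endpoints (four lead safety, one MRI safety, four MRI efficacy), and all nine must succeed. If the set is followed as written, an investigational RA lead no better than the criterion could pass almost automatically. If it is quietly replaced by the RA-lead set, the denominator of a primary safety endpoint is being chosen outside the plan, possibly after data are seen.

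**Working it through.** **Inputs.** Criteria 92% (acute) and 95% (chronic); planning rates 0.97 and 0.98; registry RA rates 0.995 and 0.996; one-sided 2.5%, applied as the lower limit of a two-sided 95% log-log interval exceeding the criterion; 800 RV and 400 RA leads (all from 4.2.1). Total of 800 patients and at least 30% with an RA lead, i.e. 0.30 × 800 = 240 (4.1).

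**Assumptions.** No censoring in the main calculation; no RA-lead complication in a patient without an RA lead; true RA-lead freedom exactly at the criterion for type I error.

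**Decision rule.** With *k* events in *n* patients, S = 1 − k/n, se = √[k/(n(n−k))] / |ln S|, and the lower limit is S^exp(1.96·se).

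- n = 800, k = 48: S = 0.94, se = 0.144, limit 0.9212 (passes 92%). At k = 49 the limit is 0.9198 (fails).
- n = 800, k = 27: S = 0.96625, se = 0.192, limit 0.9512 (passes 95%). At k = 28 it is 0.9497 (fails).
- Largest passing counts, acute/chronic: 21/11 at n = 400 and 10/5 at n = 240.

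Exact Clopper-Pearson limits give the same cut-offs at n = 240, 400 and 800.

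**The plan's own power.** P(X ≤ k), with X binomial at the planning rates:

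- RA, n = 400: acute P(X ≤ 21 | 400, 0.03) = 99.5%; chronic P(X ≤ 11 | 400, 0.02) = 89.0%.
- RV, n = 800: acute above 99.9%; chronic P(X ≤ 27 | 800, 0.02) = 99.6%.

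These agree with the stated figures (above 98% acute; above 98% RV and above 85% RA chronic). If the RA set were all 800 patients, 400 with an RA lead, chronic RA power would be P(X ≤ 27 | 400, 0.02), above 99.9%. The lower RA figure in the plan therefore reflects an RA-lead denominator.

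**Type I error on the literal set.** The denominator is 800, but events arise only in the *m* patients with an RA lead. P(pass) = P(X ≤ 48 | m, 0.08) acute and P(X ≤ 27 | m, 0.05) chronic.

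| RA leads among 800 | Acute | Chronic |
|---|---|---|
| 240 | >99.9% | >99.9% |
| 400 | 99.8% | 95.2% |
| 480 | 95% | 77% |
| 560 | 72% | 47% |
| 640 | 35% | 21% |
| 720 | 10% | 7% |
| 800 | 1.9% | 1.7% |

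At 400 RA leads, a lead exactly at the criterion has an apparent freedom of 1 − 0.08 × 400/800 = 96.0% acute and 1 − 0.05 × 400/800 = 97.5% chronic. The literal rule would still pass an observed RA-lead freedom of 1 − 48/400 = 88.0% acute and 1 − 27/400 = 93.25% chronic, both below the criteria.

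**Type I error on the RA-lead set.** With n = 400: P(X ≤ 21 | 400, 0.08) = 2.2% and P(X ≤ 11 | 400, 0.05) = 1.9%.

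**Censoring.** The documents give no drop-out rate. A Kaplan-Meier simulation (20,000 runs) with assumed drop-out of 5% acute and 10% chronic gives, on the literal set, 99.8%/94.6% at 400 RA leads, 73%/47% at 560 and 11%/8% at 720; on the RA-lead set at 400 it gives 1.9%/1.7%.

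**Number of RA leads.** On the RA-lead set at the 30% floor of 240, power at the planning rates is P(X ≤ 10 | 240, 0.03) = 89.0% acute and P(X ≤ 5 | 240, 0.02) = 65.1% chronic. At the registry rates it is above 99.9% for both.

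**The case against.** The best defence is that the section shows its intent. It says the endpoint is assessed and tested separately for each lead, defines the criterion as safety of the leads, and sizes the RA test on 400 RA leads. On this view the Patient Group sentence serves only to bring attempted implants into the set. Intent probably was per lead, and on that reading type I error is correct. But testing the leads separately settles which events count and how many tests there are, not who is in the denominator. The only sentence on who is included says all patients, and 4.2.3 shows that a lead condition was written where one was wanted.

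Three narrower objections stand in part:

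- The inflated rates are conditional on the literal reading and on the RA share, which the plan fixes only as at least 30%; hence the range above.
- They are rates for single endpoints. The RV tests and all other primary endpoints must also pass, so the chance of false overall success is lower. That does not protect against a problem confined to the RA position.
- The 240-lead power point is secondary. It combines the floor with deliberately conservative rates, and 400 of 800 is consistent with the 30% expectation.

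It could also be said that the RV group has the same gap, for a patient whose only Tendril MRI lead is in the atrium. Under 4.4.2.1 that would be a deviation and likely rare.

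**Conclusion.** The concern holds: the RA analysis set is wrong as written and conflicts with the power basis in the same section. Followed literally, with 800 patients, 400 RA leads, no censoring and true RA-lead freedom at the criterion, the RA tests pass with probability 99.8% (acute) and 95.2% (chronic) instead of at most 2.5%. The error rate approaches nominal only when nearly all patients have an RA lead, and moderate drop-out does not change the conclusion. If the set is limited to RA-lead patients, type I error is controlled; what remains is that the stated power depends on reaching 400 RA leads, which the completion rule does not secure. This must be fixed, because it decides the denominator of two primary safety endpoints.

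**What to change.** In 4.2.1.1 and 4.2.1.3, define the RA Patient Group as patients in whom implant of a Tendril MRI lead in the right atrium was attempted or successful. Keep the present group for the RV endpoints (4.2.1.2 and 4.2.1.4).

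In the sample-size text, add one sentence saying that RA power is conditional on 400 RA leads and giving the figure at the 30% floor: with 240 leads, about 89% acute and 65% chronic at the conservative rates, and above 99.9% at the registry rates.

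The cost is rewording two Patient Group paragraphs and adding one sentence on power. No new data, visits or patients are needed.
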